### Revision History

Ver. No.	Date	Comment
1.0	17 August 2015	For submission to 4 IRBs and regulatory agencies
1.21	27 February 2016	Incorporates recommendations from MUHAS, NIMRI, and Monitor; also adds new secondary endpoint (1.21 April 10 edit clarifies MUHAS refusal of 2 additional phlebotomies)
1.3	1 September 2016	Clarifies that this is a Phase 2b trial Clarifies replacing subjects lost to follow-up before Visit 2 Specifies concomitant medications which are exclusionary Adds 28 day patient diary Adds extra follow-up and confirmatory IGRA for new positive IGAs Adds 2.5 mL sample to be co-ordinated with final safety CBC Corrects one item in DSMB charter remaining from prior dose escalation trial Adds immune assay results from DAR-MDES Phase 1 trial in the US Adds [name] as Deputy Study Director
1.4	1 January 2018	Adds additional IGRA test with consent/assent (Table 1) Revises time of blinded endpoint analysis (2.4.2) Clarifies efficacy population as ITT population (2.8.1) Specifies active TB as an exploratory endpoint (2.8.3) Defines active TB as an SAE (12.1.3) Clarifies that borderline or invalid 2 month IGRA confers ineligibility (14.3) Revises Clinical and Deputy Study Directors (17)

## 2. PROTOCOL SYNOPSIS

### 2.1 Protocol Information

Protocol Number:	DAR- 901- PIAT
Protocol Title	A Phase 2, Randomized, Placebo-Controlled, Double-Blind, Study of the Prevention of Infection with Mycobacterium tuberculosis Among Adolescents Who Have Previously Received BCG
Sponsor:	Dartmouth College, Hanover, NH
Name of Finished Product	DAR-901 for Injection
Name of Active Ingredient	DAR-901
Phase of Development	2b
Indication (Target)	Prevention of infection with Mycobacterium tuberculosis in adolescents previously vaccinated with BCG.
Number of Subjects	650 in planned dose groups
Number of Sites	One site in Dar es Salaam, Tanzania

### 2.2 Study Objectives

#### 2.2.1 Primary Objective

To determine the safety and efficacy of a 3 dose series of DAR-901 for the prevention of infection with *M. tuberculosis* (TB) among healthy adolescents in Tanzania previously immunized with BCG.

#### 2.2.2 Secondary Objectives

To identify risk factors for infection with TB among adolescents in Tanzania.

To identify subject characteristics associated with vaccine induced protection against infection with TB.

### 2.3 Rationale for the Current Study

Development of an improved vaccine for the prevention of tuberculosis is a major international health priority. BCG (bacillus Calmette-Guerin) is almost universally administered in childhood in countries with endemic tuberculosis including Tanzania. However, vaccine-induced protection against TB wanes in adolescents and young adults. A major current emphasis is the development of a vaccine that would enhance BCG-induced immunity in both these populations. Inactivated *Mycobacterium obuense* DAR-901 represents a candidate vaccine designed to fulfill this “prime-boost” strategy in the prevention of TB.

The natural history of TB proceeds from initial infection, typically asymptomatic and identified by a positive tuberculin skin test or positive interferon gamma release assay (IGRA), to overt symptomatic disease. Among 100 persons with asymptomatic latent TB infection approximately 10% eventually progress or reactivate to develop symptomatic active TB disease. Traditional efficacy trials for the prevention of TB have used active TB disease as the primary trial endpoint. IGRA assays, which are unaffected by most TB vaccines, including BCG, now make it possible to test whether a candidate TB vaccine prevents TB infection. A recent meta-analysis of 9 published studies using IGRAAs have shown that BCG prevents TB infection (1). Prevention of Infection (POI) trials are now being considered for evaluating candidate TB vaccines (2) The present trial will be a DAR-901 prevention of infection trial in adolescents.

In previous studies, we have demonstrated the safety, immunogenicity, and efficacy of a 5-dose series of inactivated *Mycobacterium obuense* SRL 172, a whole-cell vaccine derived from a environmental non-tuberculous mycobacterium and prepared using organisms grown on agar and then heat-inactivated. Phase I safety studies were conducted in HIV-negative adults and HIV-positive adults and children in the United States, and Phase II safety and immunogenicity studies in HIV-positive adults in Zambia and in Finland.

An NIH-sponsored Phase III efficacy trial of SRL 172 was initiated in Tanzania in 2001 (hereafter referred to as the “DarDar Trial”). A total of 2013 HIV subjects with prior BCG were randomized 1:1 to receive a 5-dose series of vaccine (1 mg in 0.1 mL) or placebo (buffered saline alone) administered intradermal in the deltoid) at 0, 2, 4, 6, and 12 months. Subjects were followed every 3 months for the development of tuberculosis. The vaccine was safe and well-tolerated with minimal local reactions, 0.3% vaccine site sterile abscesses and 0.4% self-limited generalized rashes. Compared to placebo recipients, vaccine recipients showed significant increases in IFN- $\gamma$  responses to the vaccine antigen and significant increases in antibody to lipoarabinomannan (LAM). In 2008 the trial was stopped after the DSMB concluded that SRL 172 had shown significant protection against active tuberculosis (defined as “definite” tuberculosis supported by smear or culture evidence of infection) (3).

The agar-based manufacturing method used to prepare inactivated *M. obuense* SRL 172 scaled poorly. A new broth-based manufacturing process was developed at the Aeras (Rockville MD), starting from the Master Cell Bank for SRL 172. The broth-produced product, now designated *M. obuense* DAR-901, completed non-clinical immunogenicity, toxicology and challenge studies. An IND was obtained from FDA in January 2014 ([name], Principal Investigator) and a Phase I multiple- dose-escalation trial (DAR-901 MDES) among 59 HIV-negative and HIV-positive subjects with prior BCG is nearing completion in the United States. DAR-901 MDES has demonstrated that a 3 injection series of the vaccine is safe and well-tolerated in HIV-negative and HIV-positive adults with prior BCG immunization and does not affect results of an IGRA assay. An intradermal dose of 1 mg was selected by the external Dose Review Committee for further trials.

The present Phase II study will obtain preliminary data on the efficacy of a 3-injection booster series of DAR-901 in preventing TB infection among adolescents in Tanzania who received BCG at birth. The trial is designated DAR-PIA for DAR-901 Prevention of Infection in Adolescents.

## 2.4 Study Design

This is a Phase II 3-injection randomized, controlled trial of DAR-901 to be conducted in 13-15 year old adolescents in Tanzania previously immunized with BCG. The goals are to establish the safety and efficacy of DAR-901 in preventing infection with TB. The 1 mg level corresponds to the dose of SRL 172 used in the successful DarDar Trial.

Doses will be administered by intradermal (ID) injection in the deltoid area at 0, 2 and 4 months. In the Phase 2 study of SRL 172 conducted in Finland, significant immunogenicity was induced by 3 injections [1]. The dose intervals and route of administration are consistent with all previous studies of SRL 172.

All subjects will be screened by the T-spot® IGRA (Oxford Immunotec, Oxford, England) for evidence of TB infection. All screened subjects will have height and weight measured and will have a structured interview to identify risk factors for TB infection (=positive IGRA). IGRA-positive subjects will be referred for further evaluation and will not be entered in the immunization phase of the trial.

It is estimated that 1000 adolescents will need to be screened to enroll a total of 650 IGRA-negative adolescents in the immunization phase of the trial. Subjects will be and randomized 1:1 to DAR-901 or saline control at 0, 2 and 4 months. IGRA testing will be repeated before dose 2, at 14 months, and again at end of study or 24 months, whichever comes first.

The risk factor study will employ a cross-sectional analysis comparing IGRA-positive and IGRA-negative adolescents at baseline (estimated 650 IGRA-negative and 350 IGRA-positive subjects). Risk factor analysis will also be conducted on subjects enrolled in the immunization phase who develop new TB infection during the study.

### 2.4.1 Enrollment Process

As part of the overall risk management plan enrollment will proceed as follows:

- All adolescent subjects will provide written assent and their parents or guardians will provide written consent. Informed consent and assent forms will be written in Kiswahili and will be explained by a study nurse.
- Urine pregnancy tests will be performed on all female subjects on the day of scheduled immunization. Those with positive tests will be excluded from further immunization but will continue in follow-up.

#### **2.4.2 Potential protocol adjustments**

The protocol is based on a sample size calculation which assumes a 7% annual risk of new TB infection in the control group and 50% efficacy in the vaccine group. A blinded endpoint analysis will be conducted by the DSMB after all subjects have had a repeat IGRA test at one year.

#### **2.4.3 Risk Management**

- All intradermal injections of study medication (DAR-901, sterile saline) will be administered by trained study personnel.
- All subjects will be observed for at least 30 minutes after each dose
- The trial will be conducted in compliance with the protocol, GCP and applicable human studies and regulatory requirements.
- Participants who consented to Protocol version 1.3 will be provided a diary to record injection site reactions after Dose 3 and monitor adverse events up to 28 days after immunization.

### **2.5 Subject selection**

#### **2.5.1 Inclusion Criteria**

To be eligible for this study, a subject must meet ***all*** of the following inclusion criteria:

1. Is age 13 to 15 years, inclusive;
2. Has completed the informed assent procedure including signing and dating the informed assent form;
3. Has had a parent/guardian complete an informed consent procedure including signing and dating the informed consent form;
4. Has received BCG as documented by presence of a scar consistent with immunization or a contemporary medical record;
5. Female subjects must have a negative urine pregnancy test within 24 hours prior to each dose of study drug;
6. Female subjects must agree to prevent pregnancy (strict abstinence or use of ***two*** of the following methods: hormonal contraceptive [oral, injectable, implanted or intravaginal ring], condom, diaphragm, spermicide, or an intra-uterine device) from Dose 1 through the treatment period and for four (4) weeks after the last injection of study drug.

#### **2.5.2 Exclusion Criteria**

A person who meets ***any*** of the following exclusion criteria will ***not*** be enrolled in the study:

1. Has a history of active tuberculosis;
2. Has previously received another investigational vaccine against tuberculosis;
3. Has had an illness consistent with acute viral or bacterial infection within the prior (2) two weeks;
4. Has significant medical disease (chronic or active within the past 6 months), including, but not limited to: cardiac disease (e.g., symptomatic congenital heart disease, unstable angina, myocardial infarction, congestive heart failure, ventricular arrhythmia), uncontrolled seizure disorder, liver disease, autoimmune or antibody-mediated diseases (e.g., lupus, rheumatoid arthritis), organ transplantation, chronic infection, uncontrolled diabetes; diseases judged by the Investigator as not clinically significant or as fully resolved will be reviewed with the Medical Monitor;

5. Has received systemic immune suppressive, stimulatory prescription drugs, or anti-retroviral therapy during the prior three (3) months
6. Has abnormal CBC values that are considered clinically significant .
7. Has clinically significant abnormal findings on vital signs;
8. Is expected to have surgery requiring general anesthesia during the study period;
9. In the judgment of the Investigator, not suitable to participate in this clinical study.

## **2.6 Treatments**

All treatments will be administered as scheduled by intradermal injection in the deltoid.

### **2.6.1 *Investigational Treatment***

A 1 mg dose of DAR-901 administered in a dose volume of 0.1 mL.

### **2.6.2 *Comparator treatment***

Inactive comparator: 0.1 mL of Sterile Saline for Injection (placebo).

## **2.7 Assessments**

The safety and tolerability of DAR-901 will be assessed using reported and observed adverse events.

## **2.8 Statistical Analyses**

### **2.8.1 *Analysis Populations***

Analysis will be performed comparing subjects by treatment assignment (DAR-901 vs. Placebo).

- *Safety Population* — all subjects who received at least one injection of study medication.
- *Efficacy Population (ITT population)* — all subjects, as randomized with a negative IGRA at enrollment and at the time of the 2 month (=dose 2) study visit. This is the Intent-to-Treat (ITT) population.

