### **2.8.2 *Safety Analyses***

Tabulation and descriptive statistics of adverse events, and vital signs.

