## **9.6 Method of Assigning Patients to Treatment Groups**

Subjects will be assigned by computer-generated randomization. Suitable randomization procedures will be established by the CRO data management and clinical services performing the protocol and approved by the Sponsor. The research pharmacist will be provided a list of treatment assignments.

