## 14. STATISTICAL METHODS

The sections below indicate the overall structure and approach to the analysis of this study. A detailed Statistical Analysis Plan (SAP) incorporating these sections below will be prepared separately and approved by the Sponsor. The SAP will define populations for analysis, outline all data handling conventions, including software, and specify additional statistical methods to be used for analysis of safety, efficacy and pharmacokinetics.

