### 14.2 Analysis Populations

- *Safety population* – all subjects who received at least one dose of the study medication.
- *Efficacy population (ITT)* – all subjects, as randomized, with a negative IGRA at enrollment and at the time of the 2 month (=dose 2) study visit. This is the Intent-to-Treat (ITT) population.

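### As worded, Section 2.8.1 groups the Safety Population by assigned treatment, and no section groups safety data by product received

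*Protocol*

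**What the plan says.** Protocol Section 2.8.1 begins with one grouping rule: "Analysis will be performed comparing subjects by treatment assignment (DAR-901 vs. Placebo". Two bullets follow. The Safety Population is "all subjects who received at least one injection of study medication". The Efficacy Population is "all subjects, as randomized with a negative IGRA at enrollment and at the time of the 2 month (=dose 2) study visit".

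Section 14.2 restates both populations without the opening sentence. Its safety bullet again gives membership only: "all subjects who received at least one dose of the study medication". Its efficacy bullet keeps the words *as randomized*.

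Section 9.6 shows what assignment means in this protocol: "Subjects will be assigned by computer-generated randomization". Section 2.8.2 describes the safety analysis as "Tabulation and descriptive statistics of adverse events, and vital signs". Section 14.4 lists the sources of safety data. Neither says how subjects are placed in arms.

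Section 14 defers detail to a separate plan: "The SAP will define populations for analysis, outline all data handling conventions, including software".

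**The concern.** Efficacy is properly compared by randomized arm. For safety the usual choice is the product received, because grouping by assignment moves a misdosed subject's events into the other column and pulls the two arms together. For a harm comparison that is the non-conservative direction.

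Safety is half of the primary objective (Sections 2.2.1 and 6.1), and Section 14.4 makes the evaluation of adverse events its primary endpoint. A reaction or serious adverse event following DAR-901 in a subject assigned to saline would be tabulated under placebo. Section 2.8.1 as worded leads to that result, and no later section reverses it.

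**Working it through.** The protocol gives no figure on this point to reproduce. The check is a comparison of text, followed by a calculation for scale.

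**Text**

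1. The opening sentence of 2.8.1 is unrestricted and stands above both bullets, so on its wording it governs both.
2. Assignment is the randomized allocation (9.6), not the product injected.
3. Receipt of an injection decides who belongs to the Safety Population (2.8.1, 14.2). It does not decide the arm in which that subject is counted.
4. Sections 2.8.2, 14.2 and 14.4 contain no rule grouping safety data by product received.
5. Section 14.2 neither repeats nor cancels the sentence in 2.8.1.

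The protocol therefore states a grouping rule that reaches safety as worded, and states no other.

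**Scale**

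Input from the protocol: 325 subjects per arm (2.8.5). The misdosing counts and event rates below are assumptions, because the protocol gives none.

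Let *a* and *b* be the true event rates on DAR-901 and on saline, and let *k* subjects in the placebo arm receive DAR-901 for the whole course. Then:

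- observed placebo rate = b + (k/325)(a − b)
- observed difference = (a − b)(1 − k/325)

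The same holds if the *k* subjects are all in the DAR-901 arm and receive saline. If *k* subjects in each arm receive the other product, the factor is 1 − 2k/325.

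| k | k/325 | 80-point difference (90% vs 10%), one arm | 80 points, both arms | 4-point difference (5% vs 1%), one arm | 4 points, both arms |
|---|---|---|---|---|---|
| 0 | 0% | 80.0 | 80.0 | 4.00 | 4.00 |
| 1 | 0.3% | 79.8 | 79.5 | 3.99 | 3.98 |
| 3 | 0.9% | 79.3 | 78.5 | 3.96 | 3.93 |
| 7 | 2.2% | 78.3 | 76.6 | 3.91 | 3.83 |

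For example, 80 × (1 − 3/325) = 79.3 and 80 × (1 − 6/325) = 78.5.

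**Rare events**

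Section 12.5.3 gives a sterile abscess rate of 0.3% with the predecessor product in HIV-infected adults. If that rate applied here, which is an assumption, 0.003 × 325 ≈ 1 case would be expected in a full DAR-901 arm. Putting one such case in the wrong column would change the picture. The chance is low: with 3 misdosed placebo subjects, 0.003 × 3 = 0.009 such cases would be expected among them.

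**The case against.** **The text allows a second reading.** The opening sentence of 2.8.1 may do no more than name the two groups to be compared. If it already fixed grouping by randomization for both populations, *as randomized* in the efficacy bullet would be redundant. Section 14.2, the full statistics section, omits the sentence. This stands as far as intent goes, so the documents do not show a deliberate choice to analyse safety by randomized arm. It does not remove the problem, since no section states the alternative.

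**The analysis plan may settle it.** Handling of misdosed subjects is a routine convention for that document, and silence in the protocol would be no finding. Section 2.8.1 is not silent, however. A plan that groups safety by product received would depart from its wording, and a plan that follows it inherits the problem.

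**Other provisions limit the consequence.** Misdosing is a subject-level deviation that must be recorded and reported (13.6). Drug accountability records are kept (9.12). The relationship of each adverse event to study drug is judged individually (12.3.3), and the DSMB may ask to be unblinded for a possibly related serious event (7.7). The planned safety analysis is descriptive, so no test result could flip. This stands: a recognised case would not disappear, although the summary table would still show it under the wrong product.

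**Counting by product received has its own flaw.** Moving a whole subject to DAR-901 after one injection also moves events that came before it. This stands, and the fix has to deal with it.

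**Conclusion.** The point holds as a low-priority correction to an analysis rule. As worded, 2.8.1 groups safety by assigned treatment and nothing in the protocol groups it by product received, though the intent is unclear. The effect is nil without misdosing and small for common events. It is relevant mainly to a rare or serious event in a misdosed subject. These sizes rest on assumed misdosing counts, assumed event rates, and the wrong product being given for the whole course.

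Two stronger readings are tempting, and the documents support neither:

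- *Each 1% of placebo subjects given DAR-901 adds about one percentage point to the placebo reaction rate.* A reader might infer this from Table 4, where erythema after the first 1 mg dose ranged from 4 to 20 mm, so every recipient had some. But Grade 1 erythema starts at 2.5 cm (Table 12-5), so that whole range lies below the lowest grade. The range after the second 1 mg dose includes 0 mm. No erythema rate after saline is given.
- *Misdosing is likely, with 650 × 3 = 1,950 injections and a pharmacist working from a list.* Section 9.6 says only that "The research pharmacist will be provided a list of treatment assignments". That is an ordinary arrangement and says nothing about an error rate.

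**What to change.** Limit the opening sentence of 2.8.1 to the efficacy population. Then state in both 2.8.1 and 14.2 that:

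- safety is summarized by treatment actually received;
- a subject who received any DAR-901 injection is analysed as DAR-901;
- for a subject given both products, events before the first DAR-901 injection are identified separately, for example in a listing.

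The statistical analysis plan should carry the same rule. If it already does, only the protocol wording needs to be aligned. The rule should be fixed before unblinding, so that it is not chosen with a particular case in view.

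The cost is a sentence or two in each of the two sections and a small amount of extra tabulation, with none if no misdosing occurs. The efficacy analysis is unaffected.

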### **2.8.2 *Safety Analyses***

Tabulation and descriptive statistics of adverse events, and vital signs.

### **2.8.3 *Efficacy Analyses***

The efficacy analysis will include all subjects with a negative IGRA at enrollment and a second negative IGRA at 2 months.

The primary endpoint is the difference in the rate of new TB infection in two treatment groups. New TB infection is defined as conversion from IGRA-negative at 2 months to IGRA-positive at any time later in the study.

The secondary endpoint is the difference in the rate of persistent new TB infection in the two treatment groups. Persistent new TB infection is defined as new TB infection which remains IGRA positive on a second IGRA test 3 or more months later.

Although the rate of active tuberculosis disease is expected to be very low it will be analyzed as an exploratory endpoint.

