### **2.8.4 *Risk factor Analyses***

Data will be analyzed using descriptive and analytic statistics. Variables will include household or community contact with TB, residence or exposure to congregate settings such as hospitals, correctional facilities, nursing homes, and orphanages; room size; ventilation systems (windows); airflow patterns; use of public transportation (e.g. daladala buses); socioeconomic status, nutritional status, and underlying disease (e.g., diabetes).

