### ***2.8.5 Determination of Sample Size***

The sample size of 650 subjects (325 in each treatment group) is based on an expected 7% annual IGRA conversion rate among placebo recipients who remain IGRA-negative at 2 months (pre-dose 2; IGRA conversions before dose 2 may represent TB infection acquired prior to the dose 1). The sample size is calculated with 80% power to detect vaccine efficacy of 50% in preventing TB infection. Loss to follow-up is estimated at 5-10% per year. A blinded interim analysis will be conducted after results of the 14 month IGRA are available on 200 subjects. The study duration and number of repeat IGRAs will be increased if needed to detect sufficient endpoints.

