**Table 2. Study Timeline**

Month	0-4	5-8	9-12	13-15	17-20	22-24	24-36
Recruitment	X						
Risk factor analysis	X					X	X
Immunization	X	X					
Interim analysis				X			
IGRA testing	X			X		X	X
Data analysis							X

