### 14.1 Power and Sample Size

Our data from Tanzania indicate that rates of TB infection defined by a positive tuberculin skin test increase from 0% at birth to approximately 70% in adulthood (14). Data from South Africa using an IGRA to define TB infection indicate that approximately 30% of 12-14 year olds already have TB infection, and that 7-14% develop new TB infection each year (15-17). Since adult rates of TB infection as measured by tuberculin skin test surveys are similar in Tanzania and South Africa, we estimate conservatively that Tanzanian adolescents have an annual rate of new TB infection of 7% per year as defined by conversion of an IGRA from negative to positive. We hypothesize that a DAR-901 booster regimen will be 50% effective in preventing new TB infection among adolescents in Tanzania.

We anticipate identifying 650 IGRA-negative 13-15 year olds by screening 1000 subjects in this age range. Assuming a 7% annual rate of infection, and 5% loss to follow-up per year, 650 subjects randomized to vaccine or placebo and followed for an average of 1.75 years will provide 80% power to detect vaccine efficacy of 50%.

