### 14.3 Statistical Methods

The statistical analysis is divided into two parts.

1) *Risk factors for TB infection.* All screened subjects will be included in this analysis which will compare subjects who test positive for IGRA at baseline and those who test negative. Demographics, behavioral and epidemiologic risk factors, and other questionnaire items will be compared. Pearson chi-square, Fisher's exact, t-test and Wilcoxon-Mann-Whitney tests will be used as appropriate.

2) *Effect of DAR-901 vaccine on preventing new TB infection.* New TB infection is defined as conversion from a negative IGRA at 2 months after enrollment (first dose of vaccine) to a positive IGRA at any time thereafter. Subjects who convert from IGRA negative at screening to positive indeterminate or invalid at 2 months (administration of study dose #2) will be assumed to represent TB infection acquired before administration of study dose #1 and will be excluded from the endpoint analysis. All other subjects who complete the visit for dose #2 and remain IGRA negative will be included. The primary endpoint is time to new TB infection (= new IGRA-positivity), subject to right censoring. The primary test statistic will be a log-rank test comparing the two study arms (intention-to-treat), with  $p < 0.05$  defined as significant. The proportion converting over time will be calculated using Kaplan-Meier statistic. To account for the interval censoring in the capture of IGRA conversion, we will apply methods for discrete time-to-events. The secondary endpoint is time to persistent new TB infection (= new IGRA-positivity which remains positive on a second IGRA at  $\geq 3$  months later) and analysis will be conducted using the same methods described above.

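### The primary log-rank test in Section 14.3 is unadjusted although a baseline TB-exposure interview exists for every subject; stratifying on it is an optional, low-cost and small gain

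*Protocol*

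**What the plan says.** Section 2.8.3 defines what is compared: "The primary endpoint is the difference in the rate of new TB infection in two treatment groups". It does not name a test. The test is in Section 14.3: "The primary test statistic will be a log-rank test comparing the two study arms (intention-to-treat", with significance at p < 0.05. The same section adds: "To account for the interval censoring in the capture of IGRA conversion, we will apply methods for discrete time-to-events". Neither sentence names a covariate or a stratification factor.

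Baseline exposure data are collected on everyone. Section 2.4 gives each screened adolescent a structured risk-factor interview with height and weight, and Table 1 places it at screening. Section 2.8.4 lists its content: "Variables will include household or community contact with TB", then congregate settings, housing, transport, socioeconomic and nutritional status, and underlying disease. The protocol uses these data to compare IGRA-positive with IGRA-negative subjects at baseline, to study risk factors for new infection during the trial, and for the secondary objective on characteristics associated with protection. It gives them no role in the primary vaccine comparison.

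Section 9.6 says that assignment is computer-generated under procedures to be set up by the CRO. It states no stratification factor.

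**The concern.** The trial is small in events. If TB contact predicts IGRA conversion, an unstratified comparison leaves some power unused and leaves the estimate open to chance imbalance in contact between the arms. The information needed to deal with both is already collected before the first dose, and no further subject, visit or test would be required. The question is how much is really left unused.

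**Working it through.** **Inputs from the protocol.** 650 subjects, 325 per arm (Section 2.8.5). Section 14.1: "Assuming a 7% annual rate of infection, and 5% loss to follow-up per year", and "followed for an average of 1.75 years will provide 80% power to detect vaccine efficacy of 50" per cent. Sidedness is not stated; two-sided 5% is assumed below. The prevalence and prognostic strength of TB contact are not given, so a range is assumed.

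**Step 1: the plan's own 80%.** Treat 1.75 years as person-time already net of loss, with hazards from annual risks of 7% and 3.5%:

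- Control hazard −ln(0.93) = 0.0726 per year; vaccine hazard −ln(0.965) = 0.0356 per year; HR = 0.491.
- Events = 325 × 1.75 × (0.0726 + 0.0356) = 61.5.
- Schoenfeld power = Φ(½ × √61.5 × |ln 0.491| − 1.96) = 79.7%.

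So 80% can be reproduced. If 1.75 years is instead the maximum follow-up, with 5% annual loss (hazard 0.0513) and HR 0.5, the expected proportion converting in each arm is λ/(λ+μ) × [1 − exp(−1.75(λ+μ))]. That gives 11.42% and 5.89%, so 325 × (0.1142 + 0.0589) = about 56 events. Two-sided power is then 73.9% (Schoenfeld) or 70.5% (Freedman). The simulations below use this second, stricter setting.

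**Step 2: unadjusted against stratified log-rank.** Simulated trials of 650 subjects, 1.75 years, 5% annual loss, HR 0.5; 6,000 to 10,000 trials per row.

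| Assumed baseline predictor | Unadjusted | Stratified | Gain (points) |
|---|---|---|---|
| Yes/no, 10% exposed, rate ratio 1.5 | 72.8% | 72.8% | 0.0 |
| Yes/no, 10% exposed, rate ratio 2 | 72.4% | 72.7% | 0.3 |
| Yes/no, 10% exposed, rate ratio 3 | 70.9% | 71.6% | 0.7 |
| Yes/no, 10% exposed, rate ratio 5 | 68.0% | 70.9% | 2.9 |
| Yes/no, 30% exposed, rate ratio 1.5 | 72.2% | 72.3% | 0.1 |
| Yes/no, 30% exposed, rate ratio 2 | 71.2% | 71.8% | 0.6 |
| Yes/no, 30% exposed, rate ratio 3 | 70.3% | 71.3% | 1.0 |
| Yes/no, 30% exposed, rate ratio 5 | 68.8% | 71.2% | 2.4 |
| Risk-score quartiles, log-hazard SD 0.5 | 70.6% | 70.9% | 0.3 |
| Risk-score quartiles, SD 0.75 | 67.5% | 69.4% | 1.9 |
| Risk-score quartiles, SD 1.0 | 62.8% | 65.6% | 2.8 |

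Each row assumes a different population, so only the difference within a row matters. The Monte Carlo error of a single power figure is √(0.7 × 0.3 / 6000) = 0.6 point. It is smaller for a difference on the same simulated trials, but gains of a few tenths should be read as close to nil. Rejection under no effect was 4.4% to 5.4% with either test.

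Two further sets of simulations agree:

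- With conversion seen only at IGRA visits 1.0 and 1.83 years after month 2 (3,000 trials per setting), the score gains were 0.7, 2.0 and 2.7 points. A yes/no factor gave 0.6 point (15% exposed, ratio 3) and 2.5 points (20% exposed, ratio 4).
- Another 6,000 trials per setting gave −0.1 to 0.0 point at ratio 1.5 to 2, 0.7 at ratio 3, 1.8 at ratio 4, and 0.9 to 2.8 for the score.

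Where the factor was weak or not prognostic, stratifying cost 0.1 point in one set and 0.2 to 0.4 in the other.

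**Step 3: chance imbalance.** The SD of the difference in exposed proportion is √(2p(1−p)/325): 0.0235 at p = 0.10 and 0.0359 at p = 0.30. The 95% limits are 1.96 times these, 4.6 and 7.0 percentage points. Splitting such a difference d evenly between the arms shifts the HR by the factor [1 + (p − d/2)(RR − 1)] / [1 + (p + d/2)(RR − 1)]:

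- p = 0.10: 0.959 (RR 2), 0.926 (RR 3).
- p = 0.30: 0.947 (RR 2), 0.916 (RR 3).

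That is a shift of about 4% to 8% at the edge of what chance would produce. With 37.1 and 19.1 expected events, SE(log HR) = √(1/37.1 + 1/19.1) = 0.28, so the 95% interval runs from about 0.58 to 1.74 times the estimate. The worst shift shown, |ln 0.916| = 0.088, is about 0.3 of a standard error.

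**The case against.** The strongest reply is that nothing here is wrong. An unadjusted log-rank in a randomised trial is valid, its error rate already allows for chance imbalance, and the interview data serve the stated secondary objectives. All of that stands.

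It can also be said that covariate adjustment is SAP material, since Section 14 leaves additional methods to a SAP that is not shown. This stands in part. A supportive adjusted analysis may well be there, but the primary test is fixed in Section 14.3, so making a stratified version primary means changing that section.

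Four stronger readings are tempting and are not supported:

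- **That randomisation is unstratified.** Section 9.6 does not say so. It names no factor and leaves the procedure to the CRO.
- **That imbalance in TB contact could seriously distort the result.** Step 3 puts the shift at a fraction of the sampling error.
- **That the gain is worth a definite number of subjects.** Using the squared ratio of (z for power + 1.96), the score with SD 0.5 equals about 11 extra subjects in the 3,000-trial runs (71.6% to 72.3%). In the larger runs (70.6% to 70.9%) it equals about 4: (2.509/2.502)² = 1.006, times 650. For a yes/no factor with ratio 1.5 it is essentially none.
- **That a risk score fitted to the screening IGRA results would deliver the tabulated score gains.** The simulations take the score as known. A fitted score carries estimation error and predicts past cumulative infection, not new conversion among those still negative. Table 2 also marks "Risk factor analysis" in months 22-24 and 24-36 as well as 0-4, so an early locked score is not something the protocol promises.

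**Conclusion.** The point holds as an optional efficiency improvement. Section 14.3 fixes an unadjusted primary comparison while a baseline exposure interview is available for every subject and has no role in it. Stratifying would add about 0 to 1 percentage point of power for a moderate predictor (rate ratio up to 3, or score SD 0.5) and about 2 to 3 points only for a strong one. If the factor is not prognostic, it costs about 0.1 to 0.4 point.

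These sizes rest on assumed prevalence and prognostic strength, a two-sided 5% test and roughly 56 events. A reader might infer that the primary test is invalid or biased; it is neither.

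Other open inputs move power as much or more. The unstated sidedness changes the Schoenfeld figure from 73.9% to 83.0%. Section 2.8.5 says "Loss to follow-up is estimated at 5-10% per year" where Section 14.1 uses 5%, and 10% loss lowers 73.9% to 71.9%.

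**What to change.** In Section 14.3, before unblinding:

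- State that the primary log-rank test is stratified by household or community TB contact (yes/no) as reported at the screening interview. Later interviews in Table 1 come after randomisation and should not be used.
- Put subjects with a missing answer in a fixed, pre-specified category so that none drop out of the comparison. Section 14.6 says that missing data will in general not be imputed, so the rule has to be written down.
- Include the same term in the discrete-time model.
- Keep the unadjusted log-rank as a sensitivity analysis.

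The simple yes/no factor is preferable to a fitted score, which adds a modelling step whose loss has not been quantified.

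The cost is a few sentences, with no new data and no further subjects. There are two downsides: the estimated efficacy becomes conditional on the factor, and power falls trivially if the factor turns out not to predict conversion.
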